## **SAMPLE SIZE AND DATA ANALYSIS**

### **Sample Size**

The DISS will serve as our primary endpoint, and the power/sample size analysis is based on this primary endpoint. Our mixed model approach depends on the size of the intra class correlations (ICC) between repeated measures. Based on results from our prior research), with a sample size of 20 completers each arm and 20% attrition rate, we would have the power of 0.92 to detect a medium effect size of Cohen's  $d=0.5$  based on simulation analysis at the  $\alpha$  level of 0.05. Given the measurement sensitivity of our approach, we anticipate sufficient power to detect differences between groups for both cognitive and sleep outcomes.

Multiple corrections will be performed at the critical p-values of 0.05, 0.025, and 0.017 to show minimum and maximum sensitivities using the false discovery (FDR) method, which

is contingent upon the number of outcome measures that exceed these given critical values.

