#### Main Analysis

The Primary Endpoint (PE) is the between-group difference (SUV vs PBO) in each DISS subscale at four EMA time-of-day assessments (Morning, Midday, Afternoon, Evening) across the study period. Based on our current MISP, we anticipate high adherence with >80% completion of all assessments. We will fit linear mixed-effects models for each subscale, including fixed effects for Group, Time of Day, Day (1–16 continuous), age, and sex; and a random intercept for each participant. The Group×Time interaction will be evaluated using a 4-degree-of-freedom Wald test to determine whether suvorexant and placebo differ at any time of day. If needed, the generalized additive model (GAM) will be used to account for the non-linear time effects. Covariates will be limited to age and sex at birth. Multiple imputation will be implemented for missing data; to confirm the assumptions of multiple imputation that data is missing at random, we will perform sensitivity analyses.

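### If participants differ stably in their time-of-day pattern, the random-intercept-only primary model makes the 4-df joint Wald test reject too often

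*Combined protocol and SAP*

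**What the plan says.** Four surveys a day for 16 days (Daily Survey Completion) give 64 records per participant, 16 at each time of day. The Main Analysis defines the endpoint: "The Primary Endpoint (PE) is the between-group difference (SUV vs PBO) in each DISS subscale at four EMA time-of-day assessments". The fixed effects are followed by "and a random intercept for each participant", and the Group×Time interaction is then "evaluated using a 4-degree-of-freedom Wald test to determine whether suvorexant and placebo differ at any time of day".

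The plan names no participant-by-time term, residual correlation structure, clustered variance or small-sample df method. The optional GAM concerns non-linear time effects. On missing data the plan says "Multiple imputation will be implemented for missing data" and "we anticipate high adherence with >80% completion of all assessments", but names no imputation model. Secondary Analyses applies the same model to fatigue/sleepiness and to positive and negative affect.

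Sample Size says "Our mixed model approach depends on the size of the intra class correlations (ICC) between repeated measures" but gives no ICC. Its power statement is for a trial "with a sample size of 20 completers each arm and 20% attrition rate". The claim, which rests on a simulation that is not described further, is that "we would have the power of 0.92 to detect a medium effect size", taken as d = 0.5.

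**The concern.** A random intercept moves a participant's whole day up or down. It cannot represent one person who is regularly worse in the morning and another who is regularly worse in the evening. If such patterns persist over the 16 days, the model counts up to 16 repeats of one person's pattern as independent information about how the group effect changes over the day.

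The joint test is the plan's stated way to decide whether the arms differ. A chance imbalance between small arms in daily rhythm could then be read as a drug effect on a DISS subscale or on a secondary EMA endpoint. The FDR step in Sample Size takes the p-values as given and cannot repair them.

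**Working it through.** **Inputs.** From the documents: 20 completers per arm, 16 days × 4 surveys, d = 0.5, α = 0.05, about 80% completion. Assumed, because the documents give none: all variance components. Total variance is 1 = v_p (participant, the ICC) + v_pt (stable participant-by-time) + v_d (participant-by-day) + v_e. The Wald test is referred to chi-square (critical value 9.488 on 4 df).

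**1. The plan's power of 0.92.** For a uniform effect with v_pt = v_d = 0, the noncentrality is λ = (20/2)(0.5²)/[ICC + (1−ICC)/64] = 2.5/[ICC + (1−ICC)/64].
- One measure per person: λ = 2.5, and power is Φ(√2.5 − 1.96) = 0.35.
- 1-df test, ICC 0.21: λ = 2.5/0.2223 = 11.2, power 0.92.
- 4-df test, ICC 0.14: λ = 2.5/0.1534 = 16.3, power 0.92.

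Without the ICC, 0.92 can be neither confirmed nor refuted. ICC 0.14 is the nearest anchor for the 4-df test.

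**2. Error of the between-time contrasts (balanced data).** Each participant has 63 within-person df: 3 between times, 15 between days and 45 remaining. Their expected mean squares are v_e + 16v_pt, v_e + 4v_d and v_e.
- True between-time error: v_e + 16v_pt.
- Residual that the planned model pools: v_e + (48v_pt + 60v_d)/63.
- The first exceeds the second when 960v_pt > 60v_d, that is, v_pt > v_d/16.

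**3. Worked case: ICC 0.14, v_d = 0.** With r = true/pooled, the joint test rejects with probability of about P(r·χ²₃ + χ²₁ > 9.488).

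| v_pt | v_e | true | pooled | r | approximate | simulated |
|---|---|---|---|---|---|---|
| 2% | 0.84 | 1.16 | 0.855 | 1.36 | 11% | 12% |
| 5% | 0.81 | 1.61 | 0.848 | 1.90 | 22-23% | 23% |
| 10% | 0.76 | 2.36 | 0.836 | 2.82 | 40% | 40% |

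At 5%, the model's standard error for a between-time contrast is 1/√1.90 = 0.73 of the true one.

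**4. Null simulations, 20 per arm, complete data, exchangeable patterns** (10,000 replicates per setting, age and sex in the model). 4-df rejection at v_pt = 0 / 2% / 5% / 10%:
- ICC 0.2, v_d 0: 0.054 / 0.124 / 0.251 / 0.426
- ICC 0.2, v_d 20%: 0.025 / 0.076 / 0.202 / 0.386
- ICC 0.5, v_d 0: 0.057 / 0.181 / 0.352 / 0.579
- ICC 0.5, v_d 20%: 0.015 / 0.094 / 0.293 / 0.547

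More participants do not help. With 20/(1 − 0.2) = 25 per arm, ICC 0.4 and v_d 0, a separate simulation gives 0.052 / 0.147 / 0.307 / 0.509.

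**5. Single-time differences (v_d = 0).** The model variance per participant is about v_p + 0.29v_pt + v_e/16; the truth is v_p + v_pt + v_e/16. At ICC 0.14 and a 10% share this is 0.216 against 0.2875, so the error is 2[1 − Φ(1.96√(0.216/0.2875))] = 9%. If people differ only in the morning, with the same average share, the Morning term is 4v_pt. The truth is then 0.14 + 0.40 + 0.0475 = 0.5875 and the error about 23%. At a 5% share it is 0.205 against 0.391, about 16%. Simulated ranges:
- Exchangeable patterns: about 6-10%.
- Morning difference under a linear daily trend or a morning-only pattern: 7-16% at a 5% share, 9-24% at 10%.
- All-day mean, exchangeable patterns: 93-96% interval coverage.

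**6. Missing surveys.** With 20% missing at random (ICC 0.2 and 0.5) and multiple imputation, the planned test rejects 7-14%, 15-30% and 34-51% at shares of 2%, 5% and 10%. Putting the person-by-time effect in the imputation model alone does not cure it: 0.164-0.301 at 5% and 0.354-0.510 at 10%.

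**7. Candidate repairs under the null, complete data.**
- F test on four participant means: 4-6% under exchangeable, trend and morning-only patterns.
- Exchangeable participant-by-time random effect with Satterthwaite F: 1-6% if the pattern is exchangeable, but about 8-10% at a 10% share if it is a trend or morning-only.
- Unstructured covariance with plain chi-square: 8.7-10.1%. Without covariates, arithmetic agrees: P(F₄,₃₅ > 9.488 × 35/(4 × 38) = 2.18) = 9%.

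**The case against.** The strongest reply is that no figure in the documents shows the condition to hold. That stands, and it makes the whole point conditional. The upper figures also come from ICC 0.5, where the planned test has simulated power of only 0.39 for a uniform 0.5 SD effect, far from 0.92. ICC 0.14 is the better anchor, and inflation there is smaller but still clear. Omitted day-to-day variance works the other way: at v_d = 20% the between-time error is overstated unless v_pt exceeds 20%/16 = 1.25%.

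The model description may be abbreviated, since it tests Group×Time without listing it. A single random effect is therefore the natural reading rather than an explicit exclusion. The imputation results rest on assumed imputation models. The Specific Aims call the work preliminary, which limits the consequences.

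Against this, exactly zero person-by-time variance is hard to presume. Daily Survey Completion lets participants choose when surveys start, so a given time-of-day label can mean a different clock hour for different people throughout the study.

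A reader might infer that 4 df is itself a mistake. It is not: the stated purpose, a difference at any time of day, matches a joint test of four differences. Only the Group×Time label, which alone has 3 df, is loose.

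**Conclusion.** The concern holds conditionally. If stable person-by-time differences exist beyond v_d/16, the planned joint test is anti-conservative in 3 of its 4 df; a 2% share already gives about 8-18% rejection. The sizes rest on assumed variance shares, complete data and a chi-square reference, and inflation of similar order remains with 20% of surveys missing.

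Two stronger readings are tempting. One is that the trial's false-positive rate is known to be high. The documents do not support it, because they state no variance components and the test holds its level or is conservative when v_pt is zero. The other is that every group estimate from the model is unreliable. The all-day mean is nearly unaffected, and single-time differences are only mildly affected under exchangeable patterns. The Morning difference is the exception when people differ by a daily trend or mainly in the morning, so it should not be called safe in general.

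This should be changed before unblinding, so that the covariance model is not chosen from the results.

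**What to change.** In Main Analysis and Secondary Analyses:

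1. Make the primary joint test a 4-df multivariate F test on each participant's four time-of-day means, adjusted for age and sex. The equivalent alternative is a mixed model with unstructured participant-by-time-of-day covariance and a Kenward-Roger or Satterthwaite F reference. Do not use a plain chi-square reference, and do not rely on an exchangeable participant-by-time random effect alone.
2. Take single-time and between-time intervals from the same covariance.
3. Impute from a model with participant-by-time-of-day effects. With a random-intercept-only imputation model, even an analysis that includes an exchangeable participant-by-time effect rejects 8-12% at a 10% share. Pool the four differences and their covariance with a multivariate F statistic that uses the complete-data df. Check the level of this pooled test by simulation before use; it has not been simulated here.
4. State that the 4-df test is the joint test of the four group differences and that Group×Time alone has 3 df.
5. Re-run the Sample Size simulation under this model and state the variance components assumed.

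The cost is SAP wording, the re-run simulation and some power. With no heterogeneity, no day variance, complete data and a uniform 0.5 SD effect, planned Wald against means-based F gives 0.87 against 0.82 at ICC 0.15, 0.76 against 0.70 at 0.2, 0.59 against 0.51 at 0.3, and 0.39 against 0.33 at 0.5. That is a loss of 5 to 8 points, partly a legitimate small-sample correction. Between-time intervals will widen if heterogeneity exists.

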### Specific Aims

The long-term goal of this research is to improve outcomes for patients with sleep disorders. The overall objective of the current application is to test preliminarily remote monitoring and ecological momentary assessment (EMA) methods for measuring the impact of insomnia treatment on daytime symptoms (i.e., to employ EMA as an outcome measure). Based on prior research, our central hypothesis is that relative to placebo, suvorexant improves daytime insomnia symptoms as assessed via EMA.

Specific Aim 1: To employ ecological momentary assessment (EMA) methods to evaluate the impact of suvorexant on daytime insomnia symptoms among community-dwelling older adults with insomnia.

Hypothesis 1: Relative to placebo, suvorexant improves alert cognition and daytime symptoms as assessed via EMA.

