#### **Eligibility/Consenting/Phone Call**

Participants will receive the study consent form via email (or via snail mail if requested). The study team will work with potential participants to complete the informed consent process. Participants will provide their signed consent to participate in the study. Once signed consent is confirmed, participants will complete the remote assessments. Then the study staff will confirm eligibility and the sleep expert (i.e., PI) will confirm individual's study participation.

Once study participation is confirmed, the participant will be randomized to drug or placebo in a 1:1 ratio by the IDS pharmacy. Throughout the study participants will wear an actigraph. An actigraph is a wristwatch-like device that detects ambulatory movement, a validated proxy for sleep. Participants will also complete brief surveys four times per day for 16 days. At post-treatment, participants will complete validated questionnaires, neurocognitive tasks, and a brief satisfaction survey. Additional details presented below.

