### **Daily Survey Completion (Days 1-16)**

While participants wear the actigraph, they will also complete brief surveys on their mobile phones. The surveys are sent to participants 4 times a day for 16 days. Each survey takes less than 2 minutes to complete. Participants' phones will send them notifications for each survey. At the start of the study, participants will choose what time they want surveys to start. Every morning, participants will complete a survey that includes a brief sleep diary and questions about generalized quiet time activities and how they feel. Next, participants will complete three more surveys throughout the day. These surveys also ask about how they feel. These surveys will be given at random times throughout the day, about two hours apart over the next 12 hours. Study staff will be available to answer any questions or give support. Contact information for study staff and technical support will be given to them.

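### The primary model's single random intercept misstates the error of the Group×Time contrasts, in a direction the documents cannot settle

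*Combined protocol and SAP*

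**What the plan says.** The schedule under Daily Survey Completion is explicit: "The surveys are sent to participants 4 times a day for 16 days". That gives 64 surveys per participant, nested in days and crossed with four times of day.

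The Main Analysis section fits one mixed model per DISS subscale, "including fixed effects for Group, Time of Day, Day (1–16 continuous), age, and sex". The only random effect is "a random intercept for each participant". The Group×Time effect is "evaluated using a 4-degree-of-freedom Wald test to determine whether suvorexant and placebo differ at any time of day". With four times of day, 4 df can only mean the average group difference (1 df) plus three between-time contrasts of the group effect (3 df).

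Nothing else in the document addresses clustering within a day. Day is a linear trend common to everyone. The GAM fallback concerns the shape of the mean. No serial-correlation structure or robust variance is specified. The Secondary Analyses section reuses the same model for the other EMA endpoints.

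**The concern.** The central hypothesis is that "relative to placebo, suvorexant improves daytime insomnia symptoms as assessed via EMA", and the treatment acts at night. Four surveys that follow one night can be expected to share a good-day or bad-day component, and a common Day trend cannot absorb it. Participants may also differ stably in how their symptoms run over the day. The planned model puts both sources into one residual and uses that residual to judge the between-time contrasts.

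The two omissions pull in opposite directions. A shared day component cancels from a within-day contrast, so leaving it in the residual overstates the contrast's error. A stable personal time-of-day pattern does not average out over 16 days, so treating it as independent noise understates the error. At stake is the calibration of three of the four degrees of freedom of the primary test, and therefore its type I error or its power to see an effect that builds or fades over the day.

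**Working it through.** **Inputs from the documents.** 4 × 16 = 64 surveys per participant; "with a sample size of 20 completers each arm and 20% attrition rate"; participants "randomized to drug or placebo in a 1:1 ratio"; a 4-df Wald test.

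**Assumed, because the documents give no variance components.** Total variance 1; ICC 0.30, so within-person variance 0.70; day share of within-person variance 20, 30 or 40%; complete surveys; stable time-of-day pattern variance 0 to 0.03.

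**1. The plan's own figure.** The Sample Size section states power 0.92 for d = 0.5. For a comparison of participant means over 64 surveys, SD = √[(1 + 63·ICC)/64]. At ICC 0.21 this is √(14.23/64) = 0.472. The SE is 0.472 × √(2/20) = 0.149, and 0.5/0.149 = 3.35, so power is Φ(3.35 − 1.96) = 0.92. The figure is reachable, but only at an ICC the plan does not state and with a simulated model it does not describe. It says nothing about day-level variance.

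**2. Mean squares, balanced 16 × 4 layout.** Let D be the participant-by-day variance, T the participant-by-time-of-day variance and E the survey-level variance.

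- Residual of the planned model, pooled over 63 within-person df: E + (60/63)D + (48/63)T.
- Error the contrasts really carry: E + 16T.
- These are equal when (60/63)D = (16 − 48/63)T = (960/63)T, that is, T = D/16.

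**3. Ratio of planned to true contrast SE when T = 0.**

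| Day share | D | E | SE ratio | Break-even T |
|---|---|---|---|---|
| 20% | 0.14 | 0.56 | √(0.693/0.56) = 1.11 | 0.009 |
| 30% | 0.21 | 0.49 | √(0.690/0.49) = 1.19 | 0.013 |
| 40% | 0.28 | 0.42 | √(0.687/0.42) = 1.28 | 0.018 |

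Now set T = 0.02 at the 30% share, taken out of E. The planned residual is 0.47 + 0.20 + 0.015 = 0.685 and the true error is 0.47 + 0.32 = 0.79. The ratio is √(0.685/0.79) = 0.93, so the direction has reversed.

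**4. Rejection of a true null by the nominal 0.05 test** (simulation, 20 per arm, Wald against chi-square, day shares 20 / 30 / 40%).

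- As planned, T = 0: 3.0 / 2.1 / 1.6%.
- As planned, T = 0.02: 9.5 / 7.3 / 6.0%. With T = 0.03 it reaches about 14%.
- Participant-by-day added alone, T = 0.01–0.03: 10–27%.
- Both terms added: 4.6–6.1% in every setting tried.

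**5. Power, day shares 20 / 30 / 40%.**

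- T = 0, effect rising 0, 0.1, 0.2, 0.3 SD over the day: about 0.82 as planned; 0.87 / 0.91 / 0.95 with both terms.
- T = 0, effect rising 0 to 0.20 SD: 0.38 / 0.37 / 0.34 as planned; 0.48 / 0.55 / 0.62 with both.
- T = 0, constant 0.5 SD effect: a gain of only about 2–7 points.
- T = 0.02, effect rising 0 to 0.3 SD: 0.703 / 0.745 / 0.789 with participant-by-time-of-day alone; 0.703 / 0.749 / 0.795 with both. The day term adds almost nothing here.

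**6. Group difference at one time of day (30% share, T = 0).** The true variance per participant is 0.30 + 0.21/16 + 0.49/16 = 0.344. The planned model implies 0.30 + 0.21/16 + 0.49/64 + 0.69 × 3/64 = 0.353. The SE is too large by √(0.353/0.344) − 1, about 1%. For balanced data the SE of the average group difference is correct.

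**7. Incomplete surveys.** The plan expects that "we anticipate high adherence with >80% completion of all assessments". Fitted mixed models with 20% of surveys missing (participant variance 0.50, D = 0.15, 120 data sets per setting) show the same pattern. With T = 0 the model SE of a contrast was 0.088 against an actual spread of 0.076. With T = 0.03 it was 0.087 against 0.107, and about 16% of true nulls were rejected.

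**The case against.** The tempting inference from four surveys sharing a day is that the planned test is conservative and merely wastes power. The documents do not support that. It requires stable time-of-day differences between participants to be almost absent: below about 1.3% of total variance at a 30% day share. Nothing in the plan says they are. The opposite inference, that the test is certainly anti-conservative, is equally unsupported.

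Three further arguments carry weight.

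- The power gain from the day term exists only when stable-pattern variance is near zero. Beyond that, participant-by-time-of-day does nearly all the work. This stands and limits the efficiency argument.
- The effects showing the largest gains start at zero and build over the day. The plan states no such pattern, and a constant 0.5 SD effect gains little. This also stands.
- The endpoint is defined by group differences at each time of day, and these are barely touched by the day component. That is true of the individual estimates, but the 4-df test combines them, and three of its four components use the misstated error.

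None of this rescues the intercept-only structure. An error that may be too large or too small, depending on unreported variances, is a reason to specify both terms.

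**Conclusion.** The point holds in a direction-neutral form. The stated random structure does not match the design, and the error of 3 of the 4 df in the primary test is misstated. Under the assumptions above, the actual size of the nominal 0.05 test runs from about 1.6% to about 14%. It crosses from conservative to anti-conservative where the participant-by-time-of-day variance is 1/16 of the participant-by-day variance.

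The break-even follows from algebra for balanced data. The percentages rest on assumed variances and would shift with others. Whether this trial would lose power or gain false positives cannot be determined from the documents. It should be corrected before analysis, but it does not undermine the average group difference or, as far as the day component goes, the single-time differences.

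**What to change.** In the Main Analysis section, keep the participant intercept and add two random intercepts: participant-by-day and participant-by-time-of-day. State that they enter together and that a term is dropped only if its variance is estimated at zero. Participant-by-day must not be added alone, because removing day variance from the residual exposes any unmodelled stable pattern. Apply the same structure to the EMA endpoints in the Secondary Analyses section.

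The cost is about one sentence in the SAP and no new data. The downsides are an occasional zero variance estimate or convergence check, and a less favourable p-value than the planned model would give if stable time-of-day patterns are present.

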### Design

This is a single-site, double-blind, randomized, placebo-controlled clinical trial. The study employs a two-group (suvorexant, 20mg, qhs, versus placebo) parallel design and involves remote (baseline) assessments, 16-day active treatment phase with intensive ambulatory monitoring via wrist actigraphy and ecological momentary assessment (EMA). Outcome

assessments are conducted at two weeks while participants are on study treatment or placebo and include self- report questionnaires and comprehensive cognitive testing administered by computer.

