#### Secondary Analyses

To examine the effects of treatment with each secondary EMA endpoint including fatigue/sleepiness, positive affect, and negative affect, we will employ the model described above (i.e., same approach as used in the primary analysis). To examine the effects of treatment on 1) sleep continuity variables (sleep onset latency, wake after sleep onset, sleep efficiency, and total sleep time) as measured by sleep diary and actigraphy, 2) self-report questionnaires, and 3) cognitive testing, scores will be compared both within and between-groups adjusting for baseline values using analysis of covariance (ANCOVA). This procedure is known to maximize power.

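### The primary test is called a Group×Time interaction (3 df), but its stated 4 df and purpose belong to the joint test of Group and Group×Time of Day

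*Combined protocol and SAP*

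**What the plan says.** The Main Analysis section of the SAP sets the primary endpoint as the suvorexant-minus-placebo difference in each DISS subscale at "four EMA time-of-day assessments (Morning, Midday, Afternoon, Evening) across the study period". The linear mixed model for each subscale is described as "including fixed effects for Group, Time of Day, Day (1–16 continuous), age, and sex; and a random intercept for each participant". The test is then given in one sentence: "The Group×Time interaction will be evaluated using a 4-degree-of-freedom Wald test to determine whether suvorexant and placebo differ at any time of day".

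No null hypothesis or contrast is written out. The interaction is not in the list of fixed effects, and its second factor is called only Time, although the model contains both Time of Day and Day.

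Two other places bear on the point. Hypothesis 1, under Specific Aims, reads "Relative to placebo, suvorexant improves alert cognition and daytime symptoms as assessed via EMA". Under Secondary Analyses, for fatigue/sleepiness, positive affect and negative affect, the plan says "we will employ the model described above (i.e., same approach as used in the primary analysis".

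**The concern.** The name of the primary test and its degrees of freedom cannot both be right. A Group×Time of Day interaction, in a model that already has a Group term, asks whether the treatment difference is the same at all four times. The plan's stated purpose is to find out whether there is a difference at any of them. Hypothesis 1 is about improvement over placebo, not about an effect that changes through the day.

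An analyst who adds Group×Time of Day to the listed model and reads off the interaction line gets the 3-df test. That test has no sensitivity to a benefit that is constant through the day, so a real effect could be reported as null on the primary endpoint and on the secondary EMA endpoints. There is a second risk, of pairing a statistic with the wrong reference distribution. And if two readings of the primary test are still open when the data are analysed, the choice between them is not pre-specified.

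**Working it through.** **Degrees of freedom**

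Inputs: 2 arms (Design section); 4 levels of Time of Day, continuous Day, age, sex and Group (Main Analysis). The rank of the fixed-effects design matrix gives the df of each test:

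| Fixed effects | Rank |
|---|---|
| Intercept (1), Time of Day (3), Day (1), age (1), sex (1) | 7 |
| + Group | 8 |
| + Group×Time of Day | 11 |

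- Interaction alone: 11 − 8 = 3 = (2−1)×(4−1).
- Group and the interaction together: 11 − 7 = 4.

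The plan's figure of 4 therefore reproduces, but as the joint test. Writing δ for the suvorexant-minus-placebo difference at a given time, the two null hypotheses are:

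- 3 df: δ_Morning = δ_Midday = δ_Afternoon = δ_Evening (critical chi-square 7.815 at 0.05).
- 4 df: δ_Morning = δ_Midday = δ_Afternoon = δ_Evening = 0 (critical chi-square 9.488).

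A 3-df statistic judged at the 4-df critical value has actual alpha 0.023. A 4-df statistic judged at the 3-df value has 0.099.

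**Power of the two tests**

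From the plan: n = 20 completers per arm, effect size 0.5, alpha 0.05, 16 days × 4 surveys = 64 per participant, random intercept only. Assumed: total SD 1, complete data, large-sample Wald tests, and an ICC, which the documents do not give. The ICC of 0.21 used below is roughly the value at which a 1-df test of the average effect reaches the plan's power of 0.92; other values follow.

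Noncentrality splits into two parts:

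- Average part: A = mean(δ)² / {(2/n)[ICC + (1−ICC)/64]}
- Interaction part: B = Σ(δ_t − mean)² / {(2/n)(1−ICC)/16}

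The 3-df test uses B only. The joint test uses A + B.

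At ICC 0.21, the denominator of A is 0.1 × (0.21 + 0.79/64) = 0.02223, and that of B is 0.1 × 0.79/16 = 0.00494. With mean effect 0.5, A = 0.25/0.02223 = 11.24. For effects 0.42, 0.42, 0.58, 0.58, B = 4 × 0.08²/0.00494 = 5.18.

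| Effects at the four times | A | B | 3-df power | Joint power |
|---|---|---|---|---|
| 0.50 at all four | 11.24 | 0 | 0.05 | 0.77 |
| 0.46, 0.46, 0.54, 0.54 | 11.24 | 1.30 | 0.14 | 0.82 |
| 0.42, 0.42, 0.58, 0.58 | 11.24 | 5.18 | 0.46 | 0.92 |
| 0.30, 0.43, 0.57, 0.70 | 11.24 | 18.19 | 0.96 | 0.997 |
| 0.50 at one time, 0 at the others | 0.70 | 37.97 | 1.00 | 1.00 |

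For a uniform effect B = 0, so the 3-df power equals alpha at any effect size, ICC or sample size.

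**Sensitivity to the assumed ICC**

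| ICC | Uniform 0.5: 3-df | Uniform 0.5: joint | 0.42/0.58: 3-df | 0.42/0.58: joint |
|---|---|---|---|---|
| 0.10 | 0.05 | 0.98 | 0.40 | 0.99 |
| 0.21 | 0.05 | 0.77 | 0.46 | 0.92 |
| 0.30 | 0.05 | 0.61 | 0.51 | 0.86 |
| 0.50 | 0.05 | 0.39 | 0.67 | 0.84 |

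With 80% of surveys completed (12.8 days in place of 16) at ICC 0.21, the 0.42/0.58 pattern gives 0.37 for the 3-df test and 0.90 for the joint test.

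**The case against.** The best defence is that the section already identifies the test. The df, the stated purpose and the definition of the endpoint all agree, and only the label is out of line. The sentence also says the interaction will be evaluated, so it must be in the model even though the list omits it. And if Group is coded within Time of Day, with no separate Group term, the Group-by-time block has four coefficients and its 4-df Wald test is exactly the joint test. On this view the label is loose notation, and harm arises only if an analyst ignores both the df and the purpose.

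Much of this stands: the joint test is very probably what is meant. But the plan lists Group separately, and with that coding the interaction has 3 df. Another route to 4 df, Group×Time of Day (3) plus Group×Day (1), would not answer the stated question; it is conceivable only because Time is left unqualified beside a Day term.

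Two objections to the power figures are also fair. First, joint power depends heavily on an ICC the documents do not give, and 0.21 is matched to a 1-df contrast; for the joint test, power 0.92 against a uniform 0.5 needs an ICC of about 0.14. Second, the figures assume no participant-by-time-of-day variance. If that took 0.05 to 0.10 of total variance at ICC 0.21, the 0.30-to-0.70 pattern would give 3-df power of 0.73 to 0.54 instead of 0.96, against joint power of 0.96 to 0.92. The low-loss end is therefore less secure than the first power table suggests. Neither point changes the df count or the 0.05 for a uniform effect.

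**Conclusion.** The concern holds, and should be fixed before analysis. As written, the primary test contradicts itself: the named interaction has 3 df, while the stated 4 df and purpose are those of the joint test. The name is most likely the error. This rests only on the two arms, the four times of day and the separate Group term.

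The consequence depends on which test is run. If it is the joint test, nothing is lost beyond clarity. If it is the 3-df test, the loss runs from total, for a benefit that is equal all day, to negligible, for one that varies strongly over the day. The intermediate figures rest on the assumed ICC, a random intercept as the only source of correlation, and large-sample tests.

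The power of 0.92 under Sample Size cannot be tied to either test, because neither the ICC nor the simulated contrast is given. The 3-df test could not reach it for a uniform effect.

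**What to change.** In Main Analysis:

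1. Add Group×Time of Day to the listed fixed effects, written in full so that it cannot be confused with Day.
2. State the primary null for each subscale: the suvorexant-minus-placebo difference is zero at all four times of day.
3. Name the test the 4-df joint Wald test of Group and Group×Time of Day.
4. Report the four time-specific differences with 95% CIs. A multi-df Wald test shows no direction, and Hypothesis 1 is directional.
5. If a 3-df interaction test is also kept, label it only as a test of whether the effect varies over the day.

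Secondary Analyses takes up the change by reference. The cost is a few sentences in the SAP and four estimates with intervals per subscale in the report; data collection does not change. If the 0.92 under Sample Size was simulated for another contrast, it should be restated for the joint test, with the ICC given.
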